**Medtronic** 

#### 22.3. Notification of Adverse Events

#### Sponsor Notification:

The investigational center staff must report all AEs to Medtronic in a timely manner. All Severe Hypoglycemia, DKA, SAE, and SADE should be reported as soon as possible (desired within 24 hours of investigator or study coordinator awareness) to Medtronic. Refer to Table 3 below for China Investigator Reporting Requirements. For the previously mentioned events, the AE eCRF will be completed with all known details as soon as possible, this will serve as notification to Medtronic. If the study database cannot be accessed due to technical problems, contact the sponsor via email at [contact] and provide the known details of the event. Once the access issue has been corrected, the event should be entered onto an AE eCRF.

Source documents that support the event (e.g., clinic notes, hospital admission and discharge records, lab reports, EMT reports, ER/Urgent Care) should be provided to the sponsor via the Medtronic BOX safety folder. All source documents/medical records should be redacted of patient identifiers (full name, address, etc.) prior to providing to the sponsor. Each source page should be identified with the subject ID.

#### 22.4. Expedited Safety Reporting Requirements

#### **US only:**

For device studies, investigators are required to submit a report of a UADE to the sponsor and the reviewing IRB as soon as possible, but in no event later than 10 working days after the investigator first learns of the event (812.150(a)(1)).

The sponsor will notify the investigator and IRB of any event that results in a safety report per regulations to the FDA. Documentation of IRB notification of any safety event must be kept at the investigational center and a copy sent to the sponsor.

#### China only:

Sponsor submits adverse events and device deficiencies to regulatory authorities, other clinical research institutions and investigators participating in the study per local regulatory requirements and EC requirements.

Documentation of GCP office and EC notification of any safety event must be kept at the investigational center and a copy sent to the sponsor.

To EC

10976639DOC Version D Page 128 of 170

after the investigator first

learns of the event.

Per EC's requirements

#### Table 3. Investigator Reporting Requirements for AE and Device Deficiencies (China Only)

#### For the following events, reporting requirements are: **Serious Adverse Events (SAE)** Investigators shall immediately adopt appropriate therapeutic measures for subjects, and simultaneously report to the management department of medical device clinical study in investigational center in written form. Management department of medical device clinical study shall report to: Medtronic **Immediately** Within 24 hours Local food and drug regulatory authority and health and family planning competent authority of the province, autonomous region and municipality directly under the central government where the investigational center locates EC Within 24 hours/per EC's requirements For the following events, reporting requirements are: **All other AEs All Device Deficiencies** Investigators shall record all the AEs and device deficiencies occurred during the clinical study. Investigators shall analyze the reasons for the events with Medtronic and document the analysis result in written report, including the comments of continuing, suspending or terminating study, which shall be reported to the EC through management department of medical device clinical study in investigational center for review. To Medtronic Submit in a timely manner

NOTE: In case there is/are additional AE reporting requirement(s) and/or process(es) (e.g. internal hospital policy or province regulatory authority instruction, etc.), these specific AE reporting requirement and process must be documented in a separate cover.

Version D

Medtronic

Page 129 of 170

#### 22.5. Causality Assessment

10976639DOC

An AE is not automatically related to the study device or procedure simply because the subject is wearing the device and participating in the study. The event should be reviewed to determine if the device or study procedure could have possibly caused the event and therefore is related to the study device or procedure. Causality assessment is the determination of the relationship between an AE and the device being studied. It is expected that the investigational center will review all elements surrounding the AE to properly assess the causality of the event to the study device or to a study procedure.

This review would include the subjects' description of the event, study device uploads and medical records (if applicable) from the treating facility. These records will be made available to sponsor.

Investigators should classify the relationship between the AE and the study device or study procedures using one of the five possible causality categories listed below:

- **Not related:** relationship to the device or procedures can be excluded when:
  - the event is not a known side effect of the product category the device belongs to or of similar devices and procedures
  - the event has no temporal relationship with the use of the investigational device or the procedures;
  - the event does not follow a known response pattern to the medical device (if the response pattern is previously known) and is biologically implausible;
  - the discontinuation of medical device application or the reduction of the level of activation/exposure - when clinically feasible – and reintroduction of its use (or increase of the level of activation/exposure), do not impact on the serious event;
  - the event involves a body-site or an organ not expected to be affected by the device or procedure;
  - the event can be attributed to another cause (e.g., an underlying or concurrent illness/clinical condition, an effect of another device, drug, treatment or other risk factors);
  - the event does not depend on a false result given by the investigational device used for diagnosis, when applicable;
  - harms to the subject are not clearly due to use error;
  - o In order to establish the non-relatedness, not all the criteria listed above might be met at the same time, depending on the type of device/procedures and the serious event.
- **Unlikely:** the relationship with the use of the device seems not relevant and/or the event can be reasonably explained by another cause, but a relationship to the device cannot be completely ruled out.
- **Possible:** the relationship with the use of the investigational device is weak. Alternative causes are also possible (e.g., an underlying or concurrent illness/ clinical condition or/and an effect of

10976639DOC Version D Page 130 of 170

another device, drug or treatment). Cases where relatedness cannot be assessed should also be classified as possible.

- **Probable:** the relationship with the use of the investigational device seems relevant and/or the event cannot reasonably be explained by another cause.
- **Causal relationship:** the event is associated with the investigational device or with procedures beyond reasonable doubt when:
  - the event is a known side effect of the product category the device belongs to or of similar devices and procedures;
  - the event has a temporal relationship with investigational device use/application or procedures;
  - o the event involves a body-site or organ that
    - the investigational device or procedures are applied to;
    - the investigational device or procedures have an effect on;
  - the event follows a known response pattern to the medical device (if the response pattern is previously known);
  - the discontinuation of medical device application (or reduction of the level of activation/exposure) and reintroduction of its use (or increase of the level of activation/exposure), impact on the event (when clinically feasible);
  - o ther possible causes (e.g., an underlying or concurrent illness/ clinical condition or/and an effect of another device, drug or treatment) have been adequately ruled out;
  - harm to the subject is due to error in use;
  - the event depends on a false result given by the investigational device used for diagnosis, when applicable;
  - o In order to establish the relatedness, not all the criteria listed above might be met at the same time, depending on the type of device/procedures and the serious event.

#### 22.6. Anticipated or Unanticipated

If an AE is determined to be related to the study device, the sponsor will then assess the event to determine if it is anticipated or unanticipated.

- **Anticipated:** the event is identified in the CIP; labeling; report of priors/Investigator's Brochure (IB) or user guide.
- **Unanticipated:** the event has not been previously identified in the CIP; labeling; report of priors/IB or user guide.

#### 22.7. Skin Assessment: Glucose Sensor Insertion Sites

Skin irritation may be associated with the insertion of the device or device wear and may be associated with the adhesives and tapes used to secure the study devices. The area of skin associated with device

## CIP330 Clinical Investigation Plan 10976639DOC Version D Page 131 of 170 Medtronic

insertion and wear will be assessed by investigational center staff following the removal of each device. Either subject or investigational center may remove a device if they are concerned with skin irritation or skin discomfort. The Investigational Center staff will complete a skin assessment each time a study device is removed from a subject, independent of the length of time inserted or the amount of time elapsed between device removal and the assessment.

It is expected that subjects will experience mild irritation, redness, bleeding or bruising associated with the insertion and or wear of the glucose sensor and devices. These events are to be documented and captured on the Skin Assessment eCRF. An AE eCRF will only be completed if the skin assessment observation meets the following criteria:

- Infection
- Any observation that meets the criteria of moderate or severe per the skin assessment case report form (for example: bruising equal to or greater than 6 cm in longest diameter; rash that requires prescription medication)

Subjects will not be required to return to the investigational center for examination to document resolution of Skin Assessment observations. The subject should be instructed to contact the investigational center for follow-up if there is any worsening or change that concerns the subject. Worsening should be assessed to determine if AE reporting is necessary.

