## Screening and Training Period: To be completed in 30 days (Visit 1 to Visit 3)

- Visit 1: Consent and Screening
- Visit 2: Study, Device Training and Random Assignment
  - Confirm eligibility. Note that Hct eligibility criteria must be confirmed prior to Visit 2.
  - o Visit 1 and 2 can be combined if eligibility criteria are met (see note above on Hct).
- Visit 3: End of Training Period Investigational center Visit

10976639DOC Version D

Page 63 of 170

[figure not shown]
Medtronic

#### Start of Study Period: To be completed in 60 days from Visit 4 to Visit 12

- Visit 4: Phone Visit or Optional Office Visit
  - **Group A1** May be combined with Visit 5 (e.g., if sensor insertion for Day 1 is done at Visit 5)
  - **Group A2,B1, B2, C1 and C2-**Investigational center must confirm that the sensor insertion was performed at the appropriate insertion time, insertion location, and SMBG reminder.
- Visit 5: YSI™\* 1st FST
- Visit 6: Follow Up Phone Call
- Visit 7: YSI™\* 2nd FST
- Visit 8: Follow Up Phone Call
- Visit 9: YSI™\* 3rd FST
- Visit 10: Follow Up Phone Call
- Visit 11: YSI™\* 4th FST
- Visit 12: End of Study Period Visit
  - Subject has worn sensors for T= 176-188 hours.
  - Visit 11 and Visit 12 may be combined (e.g., FST occurs on Day 7 and end of the sensor wear)
  - Subjects who have new or unresolved adverse event(s) from device-related skin reactions should schedule a follow up visit 3-7 days after Visit 12.
- Unscheduled Visit: For AE Follow Up, if Required (3-7 days after Visit 12)
  - Assess for adverse events, including adverse event from device-related skin reaction ongoing at Visit 12.
  - Update adverse event form or fill in new adverse event form, as applicable.

Figure 2. Visit Schedule Subjects 14-80 years

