### **Overview of training and instructions**

#### **Investigational center staff will:**

- Train each subject on sensor insertions, removal, study devices, and study procedures
  - o Subject will be instructed to wash hands thoroughly with soap and water.
  - Subject will be instructed to clean the insertion site with alcohol and let the insertion site air dry prior to sensor insertion.
- Instruct subjects that additional OTC tape(s) (e.g. Hypafix™\* tape, etc.) may be used if needed
- Train subjects on use of CONTOUR® NEXT LINK 2.4 study meter(US only)/ CONTOUR® PLUS study meter (China only)
  - Subject will be instructed to wash his/her hands thoroughly with warm, soapy water, rinse and dry before testing blood glucose
  - Consider best practice to use "second drop" technique, express first drop and wipe away, express second drop for meter BG testing
  - Subjects will be instructed to use only the CONTOUR® NEXT LINK 2.4 study meter (US only)/ CONTOUR® PLUS study meter (China only) during the course of the study to perform study defined SMBG measurements
  - Subjects will be instructed to perform a quality control (QC) testing when a new vial of test strips is used
- Perform applicable QC testing (CONTOUR® NEXT LINK 2.4 study meter [**US only**]/ CONTOUR® PLUS study meter [**China only**]). Shake control solution bottle well prior to use.
- Instruct subjects to insert sensors in the locations according to their age. Sensors worn in the same insertion site location may be inserted on same side or opposite sides. Sensors may be inserted with the assistance of a caretaker:
  - 14-17 years
    - Arm/Arm/Buttock
    - Buttock/Buttock/Arm
  - 18-80 years
    - Arm/Arm

- Synchronize time on each Disposable Sensor (DS5) worn in-clinic by the subject using the Synergy Download Utility
- Instruct subjects to perform fingersticks (capillary SMBGs)
- Recommend subjects to set alarm (e.g., on their phone) to check their fingersticks (SBMG) at insertion, 2 hours, 10 hours, and 24 hours after insertion on Day 1 and also one approximately at the same time every day as time of the insertion
- Have subject perform the first SMBG at the investigational center or a follow up call will be required to confirm this
- Instruct subjects to wear the devices up to 7-day training period. Instruct subjects to remove the sensors (at end of training period or at investigational center) after 7 days (T= 176-188 hours).

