#### 10.2.1.4. Visit 3: End of Training Period -Investigational Center Visit

## Overview of general study procedures Investigational center staff will:

- Instruct subject to self-remove the sensors that he/she is still wearing at this visit
- Perform a Skin Assessment on the area of each of the sensor insertion sites and document in subject source and complete Skin Assessment eCRFs for each inserted sensor.

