7.9.2 Safety

Descriptive summary will be used to characterize adverse events:

- Skin assessment at sensor insertion sites
- All adverse events

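### Skin sites are assessed whatever the delay since sensor removal and summarised without regard to that delay, so the rate of mild, transient skin findings is likely biased low

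*Protocol*

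**What the plan says.** Section 22.7 asks staff to assess the skin each time a device comes off, "independent of the length of time inserted or the amount of time elapsed between device removal and the assessment". It sets no window. It also states that "Either subject or investigational center may remove a device if they are concerned with skin irritation or skin discomfort".

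For the training period, the Visit 2 instructions (Sections 10.2.1.3 and 11.2.1.3) read: "Instruct subjects to remove the sensors (at end of training period or at investigational center) after 7 days", with wear of 176 to 188 hours. At Visit 3 (Sections 10.2.1.4 and 11.2.1.4) staff are to "Instruct subject to self-remove the sensors that he/she is still wearing at this visit", which allows for sensors already off, and they assess every insertion site. The only stated limit on Visit 3 is that screening and training together finish within 30 days of Visit 1 (Sections 10.2.1.1, 11.2.1.1.1 and 11.2.1.1.2). The same sections say that "Visit 1 and 2 can be combined if eligibility criteria are met". Under Section 13.1.1, a subject who loses a training sensor early may carry on with the others; no interim assessment is described.

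Mild irritation, redness, bleeding and bruising go on the Skin Assessment eCRF. An AE form is added only for infection or a moderate or severe observation (Section 22.7).

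For analysis, SAP 7.9.2 lists "Skin assessment at sensor insertion sites" under a descriptive summary, as does protocol Section 25.10. Neither gives a split by delay, a maximum delay, or a rule for late assessments. SAP 7.7 separately summarises subject-reported wear duration and reason for removal.

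**The concern.** A site examined as the sensor comes off and a site examined days later are different measurements of the same outcome. The findings the protocol expects are mostly ones that can fade, and nothing in either document separates a site that was never affected from one that has recovered. If both enter one summary, the reported frequency mixes two quantities and tends to fall below the frequency at removal.

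Skin assessment is one of the two safety summaries listed. Section 21.4 describes the risk of insertion and wear as minor bleeding or minor skin irritation, which are the findings a late look is most likely to lose.

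**Working it through.** The documents state no expected skin-event rate, precision target or fading time, so there is no planned figure to reproduce. Two things follow from the documents: the longest permitted delay and the share of sensors exposed to it. The third step is illustration only.

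**1. Longest permitted delay.**
Inputs: 30 days from Visit 1 to Visit 3; Visits 1 and 2 on the same day (day 0); removal at 176 to 188 hours.
Delay = 30 − (day of Visit 2) − (wear hours / 24).
- Visit 2 on day 0: 30 − 176/24 = 22.7 days; 30 − 188/24 = 22.2 days.
- Visit 2 on day 7: 15.7 to 15.2 days.
- Visit 2 on day 14: 8.7 to 8.2 days.
- A training sensor lost on day 1, with Visit 2 on day 0: 30 − 1 = 29 days.

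**2. Share of sensors.**
Planned completers are 100 + 40 = 140 adults with 2 sensors each and 100 + 20 = 120 subjects aged 2-17 with 2 or 3 each. Per period that is 280 + 240 = 520 to 280 + 360 = 640 sensors. Training and study wears use the same configurations, so training sensors are about half of the 1,040 to 1,280 planned wears.

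**3. Illustration of the attenuation.**
Assume visible signs fade exponentially with half-life *h*. The fraction still visible after delay *d* is 0.5^(*d*/*h*). If a share *s* of sensors is seen after delay *d* and the rest at removal, then
observed rate / true rate = 1 − *s* × (1 − 0.5^(*d*/*h*)).

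With *d* = 2 days and *s* = 0.5 (for example, every training sensor late and every study sensor on time):

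| Assumed half-life | Still visible at 2 days | Observed / true |
|---|---|---|
| 1 day | 25% | 63% |
| 3 days | 63% | 81% |
| 7 days | 82% | 91% |
| 14 days | 91% | 95% |

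With *s* = 0.25 the ratio runs from 81% (1 day) to 98% (14 days). At a 7-day delay, the share still visible at half-lives of 1, 3, 7 and 14 days is 1%, 20%, 50% and 71%.

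**The case against.** The best case on the other side has five parts.

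*The scoring rule is not shown.* A reader might infer that a faded reaction is recorded as a clear site. The documents do not say so. The Skin Assessment eCRF is held under separate cover and might ask about history or dates, and Section 22.7 could be read as covering reactions experienced as well as signs seen. This stands: under-recording is likely, not established. Likewise, the SAP does not choose to pool; it is silent on delay.

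*Serious reactions have other routes.* AEs are elicited at every visit and call (Section 22), subjects are asked to contact the site about worsening (Section 22.7), and unresolved skin AEs at study end get a 3-7 day follow-up. A reader might infer that the bias is greatest for sensors removed because of a reaction. The documents do not support that: infection and moderate or severe reactions probably last longer and can be reported from memory. These routes do not, however, capture the mild findings, which go to the skin form alone. The follow-up visit, and the recommendation to remove sensors in the clinic (Sections 10.2.1.8 and 11.2.1.8), apply only at the end of the study period.

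*The direction is not certain for every finding.* Scab, scarring and infection, all listed in Section 21.1, may appear after removal, so a later look can add some. This stands for those findings, but not for redness, irritation or bruising.

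*Three weeks is an outer limit.* It combines same-day Visits 1 and 2 with the last permitted day for Visit 3. Visit 3 is the end-of-training visit, and the schedule figures, not shown here, may set a tighter target. This stands.

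*The rule has a purpose.* It ensures that no removed sensor goes unassessed, and the skin data carry no hypothesis or pass/fail threshold. Both are true. They argue for keeping the rule and reporting the delay, not for leaving it out.

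**Conclusion.** The point holds in a limited form. The plan permits a removal-to-assessment delay of up to about 22 days after full training wear and does not use that delay in the analysis. Mild, transient findings at sites seen late are therefore likely to be under-recorded, and the skin-assessment rate is likely biased low. Infection and moderate or severe reactions should be less affected.

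The size is unknown. The range of 63% to 95% of the true rate assumes exponential fading, a half-life of 1 to 14 days, a 2-day delay and half of all sensors seen late; none of these comes from the documents. A reader should not take the lower end as an estimate, nor the 22-day maximum as typical. The trial's pass/fail decision, which rests on sensor accuracy, is not touched.

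**What to change.** Leave Section 22.7's requirement to assess every site as it is. In SAP 7.9.2:

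- Derive the delay from removal to assessment for each sensor, using the removal timing behind the wear-duration summary in SAP 7.7.
- Report skin findings for all sensors, and separately for those assessed on the day of removal and those assessed later, by training and study period.
- Show removals for skin irritation as their own row, from the reason for removal in SAP 7.7. The examples given there are scheduled removal, adverse event and fell out. Mild irritation is not an AE under Section 22.7, so check that the coding can identify these removals.
- Keep the all-sensor rate as the main figure. The same-day rate should stand beside it, not replace it, because same-day assessments favour sensors that lasted to a clinic visit.

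The cost is one derived variable, one more table and smaller denominators in each stratum. Removal times reported by subjects will carry some error, but should be good enough to separate same-day from later. No new visits are needed.

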## CIP330 Clinical Investigation Plan 10976639DOC Version D Page 132 of 170 Medtronic

#### 22.8. Documentation of Symptoms During Frequent Sample Testing

During FST it is expected that subjects 14-80 year old may experience minor symptoms that are related to the procedure requirement of driving glucose levels high and low. Subjects who participate in exercise during the FST observation may also experience minor symptoms.

All symptoms experienced by the subject must be recorded on the appropriate log. Those symptoms that are minor and directly associated with the requirements of the FST would be recorded on the log only. Examples include:

- leg cramp or muscle discomfort related to exercise
- headache
- shakiness/tremors
- discomfort associated with IV insertion
- shortness of breath

Events that are more serious should be noted on the log and reported as AEs. This would include:

- Severe Hypoglycemia
- Diabetic ketoacidosis
- Seizure
- Vomiting
- Chest pain
- Syncope/Fainting
- Shortness of breath unrelated to physical activity

